BIOMEDICAL RESEARCH PROTOCOL

UNIVERSITY OF MISSOURI

Project Title: Differential Efficacy of Corticosteroid Solutions for Non-Operative Treatment of Digit Flexor Tenosynovitis: A Double-Blind Prospective Randomized Clinical trial.

IRB Number: 2014039

Version Number: 2.0

Version Date: 27 JUL 2020

Principal Investigator: [name]

Background:

Idiopathic stenosing tenosynovitis of the digits, more commonly known as trigger finger, is a common cause of hand pain and dysfunction. Many previous studies have described the pathophysiology of this condition and it can be summarized as inflammation of the flexor tendons leading to a size mismatch between the tendon and the flexor pulley system. By far the most common location of this mismatch is at the A1 pulley.

The current mainstay of treatment has been:

1. Injection of corticosteroid into the area immediately surrounding the A1 pulley and flexor tendon
2. Surgical release of the A1 pulley

Several corticosteroids have been used for injection- dexamethasone, methylprednisolone, triamcinolone, betamethasone, paramethasone, etc. Less commonly used treatment strategies have included: topical NSAIDs and extracorporeal shock therapy. The typical progression of treatment is one or two steroid injections and then surgical release if injections have failed.

To our knowledge, there have been no head to head comparison studies of the efficacy of different corticosteroid formulations in preventing conversion to surgical treatment. In our study, we will look at the efficacy of two of the most commonly used steroids: triamcinolone and dexamethasone.

Objectives:

Primary outcome: Treatment success, defined as lack of conversion to surgical treatment, or no desire to proceed with surgery during study period (3 months).

Secondary outcomes: Grade of triggering (Green classification of trigger finger severity¹), QuickDASH and PROMIS Upper Extremity scores, VAS.

Study Question/Hypothesis:

We hypothesize that a 0.5 cc injection of Triamcinolone 40 mg/mL will be the most effective steroid injection for the non-surgical treatment of trigger finger.

Inclusion/Exclusion:

Inclusion criteria:

1. Adults aged 18 years and older
2. At least one symptomatic trigger finger
3. Patients recommended to receive corticosteroid injections

Exclusion criteria:

1. Previous surgeries/injections for trigger fingers in digit being treated for study
2. Participating in another clinical trial
3. Inability to receive corticosteroid injections (i.e. allergies, adverse reactions, etc.)
4. Unable to sign informed consent
5. Pregnant or plan to become pregnant

Number of Subjects:

Approximately 200 subjects will be enrolled.

Study Procedures/Methods:

Enrollment/Randomization/Treatment Visit:

Eligible patients presenting with primary flexor tenosynovitis will be enrolled on a voluntary basis. Prior to the injection, subjects will have already completed the PROMIS and QuickDASH surveys as part of standard care.

Enrolled patients will be randomized to one of three treatment arms:

1. Triamcinolone 40mg/mL
2. Triamcinolone 10mg/mL
3. Soluble dexamethasone 4mg/mL

Each study patient will receive the appropriate corticosteroid injection in the affected digit(s), consisting of a 1:1 mixture of 1% lidocaine plain and corticosteroid, total volume 1cc.

Blinding:

Syringes will be prepared and masked with opaque tape by the clinic nurses, thus providing blinding for providers administering the injection.

Follow-Up/Clinic Visits:

Subjects will be re-evaluated at 6 weeks post-injection and, if still symptomatic, will undergo a second injection of the same corticosteroid solution. At final follow-up (12 weeks), symptomatic patients who have failed treatment after 2 injections will be offered surgical release of the A1 pulley. Subjects who refuse a second injection at 6 weeks follow-up will be offered surgery, and the reason for refusal (treatment failure) will be recorded.

The visits and all research activity will be outlined below:

6 Week Follow-Up:

- Objective Measures:
 - Grade of triggering (Green classification of trigger finger severity1)

- Subjective Measures:
 - QuickDASH
 - PROMIS scores
 - VAS
- Second Corticosteroid injection (if subject still symptomatic)

12 Week (3 Month) Follow-Up (if applicable):

- Objective Measures:
 - Grade of triggering (Green classification of trigger finger severity1)
- Subjective Measures:
 - QuickDASH
 - PROMIS scores
 - VAS

6 Month Follow-Up:

The patient will be contacted via a phone call or Patient IQ to check on the status of their condition. If they are still experiencing a degree of triggering they will be advised by their physician to return to clinic for a standard of care visit. If they are no longer experiencing triggering, they will be asked to complete a survey over the phone or through Patient IQ only.

Specimen Collection: If a patient is recommended to undergo surgery at the end of the study, the tendon and capsule that is normally resected and discarded after surgery will be collected for analysis. After collection these tissues and data will be identified from the patient and assigned a number for use in study analysis. **We seek to only collect tissues from patients that are normally removed and discarded during trigger finger release procedures. None of the patients will undergo additional surgical procedures for the collection of tissues in this study.** For simplification purposes, potential subjects must agree to the collection of these specimens to participate in the study, even if they do not end up needing surgical intervention.

The collected tissue will be formalin-fixed and processed for histological sectioning for routine and immunohistochemical staining to assess and score degree of tissue pathology and effects of injections on treated tissue in order to effectively test the hypothesis.

Potential Risks:

There could be risk of accidental data breach/breach of confidentiality, and this will be minimized by having patient collected de-identified data locked separate from the decoder list linking subject number to patient MRN.

Potential Benefits:

Potential benefits include relief of their trigger finger pain and function. Steroid injections have been shown to provide symptom relief for patients suffering from trigger finger. We also hope to demonstrate a differential efficacy between different corticosteroid formulations, which would help guide future clinical decision-making.

Compensation:

The subjects will not be compensated for their participation in the study.

Costs:

The subjects will be financially responsible for all of their standard of care treatment and the corticosteroid injections are considered standard of care and will be billed to their insurance.

Statistics/Power:

We define a clinically significant difference in treatment efficacy as an absolute risk reduction of surgery of 20% (NNT = 5) between steroid formulations.

Based on our power calculation, 158 patients are required to have a 90% chance of detecting, as significant at the 5% level, an increase in treatment success of corticosteroid from 70% in the control group to 90% in the experimental group.

We plan to enroll 200 subjects to account for subjects that do not complete the study or are lost to follow-up.

References:

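### The primary outcome joins its two conditions with *or* and leaves conversion undefined, so a patient who accepts surgery at the 12-week visit can be scored a success

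*Combined protocol and SAP*

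**What the plan says.** **Definition.** The Objectives section gives the only definition of the primary outcome: "Treatment success, defined as lack of conversion to surgical treatment, or no desire to proceed with surgery during study period (3 months"). The word conversion also appears in the Background, in the phrase "efficacy of different corticosteroid formulations in preventing conversion to surgical treatment". Neither place says whether it means surgery offered, accepted, scheduled or performed.

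**When surgery arises.** Follow-Up/Clinic Visits describes two routes.
- After two injections: "At final follow-up (12 weeks), symptomatic patients who have failed treatment after 2 injections will be offered surgical release of the A1 pulley".
- At week 6: "Subjects who refuse a second injection at 6 weeks follow-up will be offered surgery, and the reason for refusal (treatment failure) will be recorded".

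The later visit is headed "12 Week (3 Month) Follow-Up (if applicable"), so the protocol treats 12 weeks and 3 months as the same time point.

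**What is recorded.** The visit lists are introduced with "The visits and all research activity will be outlined below". At 6 and 12 weeks they name grade of triggering, QuickDASH, PROMIS and VAS. The 6-week list adds the second injection. Neither list has an item for wish for, or acceptance of, surgery.

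**Planning rates.** Statistics/Power states the target difference as an "absolute risk reduction of surgery of 20% (NNT = 5) between steroid formulations" and then as "an increase in treatment success of corticosteroid from 70% in the control group to 90% in the experimental group".

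**The concern.** The main failure path in this trial is two injections, persistent symptoms, and an offer of surgery at week 12. An operation that follows that offer will normally take place at or after the close of the 3-month window. Whether this patient counts as a success then depends on two things the protocol leaves open: what event counts as conversion, and whether both conditions must hold or only one.

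At stake is the classification of the primary outcome, on which the trial is sized. If the rule is settled only after outcomes are known, it becomes a post hoc choice on the primary endpoint. The answer to the surgical offer is also not named as endpoint data, so the information needed to apply the likelier rule may not be collected in a uniform way.

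**Working it through.** **1. The plan's own figure.** Inputs from Statistics/Power: success 70% v 90%, 90% power, 5% level (taken as two-sided). Unpooled two-proportion formula:

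n per arm = (1.960 + 1.282)² × (0.7×0.3 + 0.9×0.1) / 0.20² = 78.8, rounded up to 79; 2 × 79 = 158.

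This matches the stated 158 as a two-arm total. The calculation itself is not affected by this point; what is unclear is the event to which the 70% and 90% refer.

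**2. Applying the definition to each type of patient.** Three readings are possible:
- (a) conversion is an operation performed by 3 months, and either condition suffices;
- (b) conversion is the decision to operate, and either condition suffices;
- (c) both conditions are required.

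| Patient | (a) | (b) | (c) | Follow-Up/Clinic Visits |
|---|---|---|---|---|
| Fails two injections, accepts surgery at week 12, operated on later | Success | Failure | Failure | Failed treatment |
| Refuses second injection, operated on before week 12 | Failure | Failure | Failure | Treatment failure recorded |
| Refuses second injection, wants no surgery | Success | Success | Success | Treatment failure recorded |
| Symptomatic after two injections, declines surgery at week 12 | Success | Success | Success | Failed treatment |

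The first row is the ambiguity: its score changes with the reading. Reading (a) also makes the second condition redundant. A patient with no wish for surgery will not have been operated on, so already meets the first condition. Rows three and four are a separate conflict: the Objectives score these patients as successes on every reading, while the follow-up section attaches a failure label to them.

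**3. Could the effect on power be sized?** Only with inputs the protocol does not give. The figures below are illustrations: exact power of the pooled two-proportion z test, two-sided 5%, 79 per arm (158 taken as two arms).

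*Premise A: 70% v 90% are rates of neither surgery nor wish for it, but the trial is scored on operations performed.* Assume an equal share s of planned failures in each arm is operated on by 3 months. Success becomes 1 − 0.30s v 1 − 0.10s.

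| s | Success | Power |
|---|---|---|
| 1 | 70% v 90% | 90% |
| 0.7 | 79% v 93% | 75% |
| 0.5 | 85% v 95% | 58% |
| 0.3 | 91% v 97% | 37% |
| 0.1 | 97% v 99% | 10% |

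At s = 0.5 about 79 × 0.30 × 0.5 = 12 and 79 × 0.10 × 0.5 = 4 patients change class.

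*Premise B: 70% v 90% already describe operations performed by 3 months.* Scoring on operations then loses nothing. If the trial is instead scored on neither surgery nor wish, and a share w of unoperated patients wants surgery at week 12, success becomes 0.70(1 − w) v 0.90(1 − w).

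| w control, experimental | Success | Power |
|---|---|---|
| 0, 0 | 70% v 90% | 90% |
| 0.1, 0.1 | 63% v 81% | 72% |
| 0.2, 0.2 | 56% v 72% | 56% |
| 0.2, 0.1 | 56% v 81% | 93% |
| 0.1, 0.2 | 63% v 72% | 23% |

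Premise B would mean about 79 × 0.30 = 24 and 79 × 0.10 = 8 patients operated on by 3 months. The only earlier route to surgery that the protocol describes is refusal of the second injection at week 6, and no refusal rate is given.

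Across these cases power runs from 10% to 93%. Its direction and size depend entirely on s, w and the premise, none of which can be read from the protocol.

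**The case against.** **The intention is clear enough.** Only reading (a) makes the week-12 accepter a success. That reading makes half the definition redundant and conflicts with the follow-up section, and the Background describes surgery as what follows failed injections. Taken as a whole, the document points to failure. This stands: these are not two equally likely endpoints. But the sentence that defines the endpoint does not say it, and the target difference in Statistics/Power is expressed as surgery, with no mention of desire.

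**The two statements of the target are compatible.** A 20-point reduction in surgery and success of 70% v 90% are complements if surgery is the failure event. That is correct. What they leave open is whether surgery here means an operation or a decision to operate.

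**The answer to the offer will be known.** Usually it will, and the 6- and 12-week lists are not the whole outline: a 6-month contact and specimen collection follow. Even so, no item for wish for or acceptance of surgery appears anywhere.

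**The week-6 wording has another reading.** It may mean that refusing the second injection is itself classed as treatment failure. That is possible, but it would still need to be reconciled with the Objectives.

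**The power figures do not describe this trial.** This stands. They rest on assumed shares, and on 79 per arm, whereas 200 patients in three equal arms would be about 67 each (200/3). The three-arm sample size is a separate matter. A reader might infer from the low figures that the trial is underpowered because of this wording. The document does not support that, because the same exercise also gives power at or above the planned 90%.

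**Conclusion.** The point holds as a defect in the definition of the primary endpoint that should be fixed. As written, the rule can count a patient who accepts surgery at the endpoint visit as a success when the protocol elsewhere calls the same patient a treatment failure. Two further groups carry conflicting labels whichever reading is taken.

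This rests on three features of the text: conversion is undefined, the conditions are joined by *or*, and the surgical offer falls where the window closes. It needs no numerical assumption.

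It does not follow that the sponsor intends to count such patients as successes, since the context favours the opposite. Nor does it follow that power is lost. The planned 90% applies to whichever endpoint the 70% v 90% were meant for, and the protocol does not say which. The number of patients affected and the direction of any effect are unknown.

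**What to change.** 1. **Objectives.** Replace *or* with *and*: success means no A1 pulley surgery performed by the 12-week visit **and** no wish for or acceptance of surgery recorded at the 12-week endpoint; anything else is failure.
2. **Data collection.** Record wish for or acceptance of surgery as one yes/no item at 12 weeks for every patient. Because the 12-week visit is marked as applying only to some, obtain the answer remotely from patients without that clinic visit; the protocol already plans phone or Patient IQ contact at 6 months. Record the same item at 6 weeks for those who refuse the second injection.
3. **Reconcile Objectives with Follow-Up/Clinic Visits.** State how the endpoint scores (i) patients who refuse the second injection but want no surgery and (ii) patients still symptomatic after two injections who decline surgery at week 12. The definition in step 1 would count both as successes unless the sponsor states otherwise.
4. **Statistics/Power.** State that 70% v 90% refer to the endpoint so defined, or restate the planning rates and recheck the power.

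The cost is a few sentences, one extra data field, a remote contact for patients with no 12-week visit, and possibly a restated planning assumption. No change to treatment is involved.

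### Read literally, the primary outcome scores a subject who has failed two injections and accepts surgery at week 12 as a treatment success, and neither visit list records whether a subject wants surgery

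*Combined protocol and SAP*

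**What the plan says.** The Objectives section gives the primary outcome as "Treatment success, defined as lack of conversion to surgical treatment, or no desire to proceed with surgery during study period (3 months"). It does not say how the two limbs combine.

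Follow-Up/Clinic Visits describes two routes to an offer of surgery:

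- At week 6: "Subjects who refuse a second injection at 6 weeks follow-up will be offered surgery, and the reason for refusal (treatment failure) will be recorded".
- At week 12: "At final follow-up (12 weeks), symptomatic patients who have failed treatment after 2 injections will be offered surgical release of the A1 pulley".

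The same section introduces its schedule with "The visits and all research activity will be outlined below". Weeks 6 and 12 then list the Green grade, QuickDASH, PROMIS and VAS, plus the second injection at week 6 for those with symptoms. Neither list has an item for wanting, accepting or having surgery. The later visit is headed "12 Week (3 Month) Follow-Up (if applicable"), and no condition is given. The 6-month contact asks about the state of the condition and falls after the outcome window.

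Specimen Collection expects some operations to follow the trial: "If a patient is recommended to undergo surgery at the end of the study".

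**The concern.** A two-limb success definition joined by *or* is met when either limb is met. A subject who wants surgery but has not yet had it satisfies the first limb and is a success. The timetable makes this an ordinary case, because surgery is first offered to two-injection failures at the visit that closes the 3-month window.

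If the stricter reading is meant, the trial needs to know at week 12 whether each unoperated subject wants surgery. The protocol does not list that for collection. Three things are at stake:

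- Subjects whom the protocol itself regards as treatment failures could be counted as successes.
- A wish that was never asked about cannot be recovered at analysis.
- With the rule unsettled, it could be chosen after the data are seen.

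**Working it through.** **The plan's own figure.** Statistics/Power gives 158 patients for 70% v 90% success, 90% power and a 5% level. The two-sided unpooled two-proportion formula gives

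n = (1.960 + 1.282)² × (0.7 × 0.3 + 0.9 × 0.1) / 0.20² = 78.8, so 79 per group and 2 × 79 = 158.

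The figure reproduces. The point below concerns the outcome's definition, not this arithmetic.

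**Time left for surgery to count.** By the visit heading, 12 weeks is 3 months, so 0 days remain after the week-12 offer. By the calendar, 12 × 7 = 84 days and 365.25 / 4 = 91.3 days, so about 7 days remain. An operation accepted at week 12 would therefore normally fall outside the window.

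**Scoring each kind of subject.** *Literal* means either limb suffices. *Strict* means success needs no surgery and no wish for it.

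| Subject | Literal | Strict | What the protocol provides |
|---|---|---|---|
| Wanted surgery and had it within the window | Failure | Failure | No listed item for conversion |
| Not operated on, does not want surgery | Success | Success | No listed item for desire |
| Two injections, symptomatic at week 12, accepts surgery then | Success | Failure | Offer made; recording of the reply not stated |
| Refuses second injection at week 6, wants surgery, not operated on by 3 months | Success | Failure | Offer made; reason for refusal recorded |
| Symptom-free at week 6, relapses by week 12, wants surgery | Success | Failure | Neither stated offer applies; visit is conditional |

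The two readings disagree in the last three rows. The third row is the protocol's main path to surgery. In the fifth row, the subject has neither had two failed injections nor refused the second. Specimen Collection does not exclude surgery for such a subject, but nothing says that the wish for it would be asked about.

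**Why size and direction are open.** Assume that failure in the strict sense is 30% v 10%, and let f be the share of failures operated on inside the window, which is all that the literal rule counts. The documents give no value for f.

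- Equal f in both groups: the counted difference is f × 30 − f × 10 = 20f points, so 20 points at f = 1 and 10 points at f = 0.5.
- Unequal f: 0.5 × 30 − 1 × 10 = 5 points, or 1 × 30 − 0.5 × 10 = 25 points.

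The difference can shrink, grow or stay the same, depending on an unknown. These values of f are illustrations, not estimates.

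**The case against.** The strongest reply is that the literal reading cannot be what the sponsor means. It leaves the second limb with almost nothing to do, since a subject with no wish for surgery will rarely have had it. The follow-up text already speaks of failed treatment for two-injection subjects and labels week-6 refusal as treatment failure. The assumed 30% failure in the control group would also be hard to reach if only operations before week 12 counted, because week-6 refusers would be almost the only source. Accepting surgery at the week-12 visit can itself be seen as desire expressed inside the window. All of this stands as evidence of intent, and the strict reading is probably the intended one. It does not supply a rule, and the wording as written gives the opposite score.

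A second reply is that desire is not wholly unobserved. The week-12 offer draws a yes or no from two-injection failures, and the reason for refusal at week 6 is recorded. The visit lists also omit conversion to surgery, so they may be lists of clinical scales, and no case report form is among the documents. This narrows the gap. It would therefore be too strong to infer that the trial will have no information on desire. What is missing is a statement that the reply is recorded and scored, and any provision for late relapsers.

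A reader might also infer that the sizing text contradicts itself, because it sets the target as "We define a clinically significant difference in treatment efficacy as an absolute risk reduction of surgery of 20% (NNT = 5) between steroid formulations" and then powers on "an increase in treatment success of corticosteroid from 70% in the control group to 90% in the experimental group". It does not. Success of 70% v 90% is failure of 30% v 10%, a difference of 20 points, and 1 / 0.20 = 5. The sentences are complementary.

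**Conclusion.** The concern holds as a defect in the outcome's wording and in what is listed for collection. Applied literally, the definition gives the wrong score on the protocol's main route to surgery. The probable intent cannot be carried out uniformly, because the wish for surgery is not listed for collection at either visit, the week-12 visit is conditional, and late relapsers fall under neither surgery offer.

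It should be fixed, but its numerical effect is unknown. A reader might infer that the trial loses a stated amount of power or is biased towards one steroid. The documents support neither: the share of failures operated on within the window is not given, nor is how it might differ by arm. Nor is 79 per group the size of an arm here. With three arms and equal allocation (assumed), about 200 / 3 ≈ 67 subjects would be enrolled per arm before dropout. If the plan's 30% v 10% already means surgery performed within 3 months, power is unaffected.

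**What to change.** 1. Assess every randomised subject at week 12, by phone or Patient IQ if they cannot attend. Both channels are already planned for the 6-month contact.
2. At that assessment, ask everyone not yet operated on the same yes/no question: do you want surgery for any digit treated in this study? Record the answer.
3. Replace the two-limb wording with: *Treatment failure is surgical release of any study-treated digit performed by week 12, or a yes to wanting it at the week-12 assessment. All other assessed subjects are successes.*

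Using the week-12 answer settles the subject who wanted surgery at week 6 and later changed their mind. Referring to any study-treated digit settles subjects injected in more than one. Only assessed subjects can be successes, so someone not reached is not counted as one by default. The rule for offering surgery can stay as it is.

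The cost is one question, one scoring sentence and a week-12 contact for some week-6 responders who might otherwise not be seen. The observed success rate may be lower than under the literal wording.

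### Histology taken only from patients who go to surgery cannot test which steroid is most effective, although Specimen Collection says it will

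*Combined protocol and SAP*

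**What the plan says.** Under Specimen Collection, tissue is obtained "If a patient is recommended to undergo surgery at the end of the study, the tendon and capsule that is normally resected and discarded" at operation, and "None of the patients will undergo additional surgical procedures for the collection of tissues in this study". No other source of tissue is described. The specimens are to be stained and scored for pathology and "effects of injections on treated tissue in order to effectively test the hypothesis".

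The only hypothesis, under Study Question/Hypothesis, is comparative: that "a 0.5 cc injection of Triamcinolone 40 mg/mL will be the most effective steroid injection". Under Objectives, the primary outcome is success, meaning that the patient neither converts to surgery nor wants it within 3 months. Histology is not among the secondary outcomes listed there.

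Under Follow-Up/Clinic Visits, at 12 weeks "symptomatic patients who have failed treatment after 2 injections will be offered surgical release of the A1 pulley". Patients who decline a second injection at 6 weeks are also offered surgery, with the refusal recorded as treatment failure. Statistics/Power plans on 70% v 90% success. It gives no method, sample size or stated limitation for the histology.

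**The concern.** Whether a patient gives tissue is decided after randomisation, and largely by the outcome that the steroids are meant to change. Randomisation protects comparisons of everyone randomised. It does not protect comparisons among the failures of each arm when the arms fail at different rates. With no tissue from before treatment, from untreated patients or from successes, a difference between arms cannot be divided into what the injection did and what was there already.

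The hypothesis concerns which arm is most effective, so using tissue to test it means comparing arms within this subset. A histology difference in either direction, or its absence, could then be offered as evidence on efficacy when it is not.

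**Working it through.** **1. The plan's own rates.** Inputs from Statistics/Power: 70% v 90% success, 5% level, 90% power, 158 patients. Two proportions, unpooled variance, two-sided:

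n per arm = (1.960 + 1.282)² × (0.70×0.30 + 0.90×0.10) / 0.20² = 78.8, so 79 per arm and 158 for two arms.

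The figure reproduces, so the planning failure rates are 30% and 10%. They are used below as a contrast between any two arms. (158 is a two-arm total in a three-arm trial, which is a separate matter.)

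**2. Expected patients with tissue.** Assumptions: 1:1:1 allocation (the ratio is not stated), 200/3 ≈ 67 per arm, and every failure has surgery.

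- 10% failure: 67 × 0.10 = 6.7, about 7 (95% binomial range 2 to 12).
- 30% failure: 67 × 0.30 = 20.1, about 20 (13 to 28).
- With 158 completers: 158/3 ≈ 52.7 per arm, giving about 5 and 16.

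**3. Precision.** SE of a difference in means, in SD units = √(1/7 + 1/20) = 0.439. Difference detectable with 80% power = (1.960 + 0.842) × 0.439 = 1.23 SD (normal approximation). With 5 v 16 it is 1.44 SD.

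**4. Selection with no effect on tissue.** Let the tendency to fail be standard normal, with the worst fraction p of each arm failing, and let pathology correlate ρ with it. Mean pathology among failures = ρ × φ(z)/p.

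- p = 0.10: φ(1.282)/0.10 = 1.755.
- p = 0.30: φ(0.524)/0.30 = 1.159.
- Gap: 1.755 − 1.159 = 0.596 SD, multiplied by ρ.

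| Assumed ρ | Better arm looks worse by |
|---|---|
| near 0 | near 0 |
| 0.3 | 0.18 SD |
| 0.5 | 0.30 SD |
| 0.7 | 0.42 SD |

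Simulation with 2 million patients per arm gave 0.178, 0.296 and 0.417 for the last three rows. In this model a true tissue benefit smaller than the gap appears reversed: at ρ = 0.5, a true −0.20 SD shows as 0.298 − 0.20 = +0.10 SD.

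**5. Alternative: post-treatment pathology fully determines failure.** The shift that turns 30% failures into 10% is 1.282 − 0.524 = 0.757 SD. Mean among failures is 1.159 in the worse arm and 1.755 − 0.757 = 0.998 in the better arm. The observed difference is 0.998 − 1.159 = −0.16 SD against a true −0.76 SD. The direction is right, but 1 − 0.161/0.757 = 79% of the effect is lost.

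**The case against.** The strongest reply is that no histology comparison between arms is actually planned. Histology is not a listed outcome and carries no test or power claim, so this is a loose purpose clause on an add-on. It is true that no such comparison is spelled out. But the section never calls the work exploratory, it makes agreement to specimen collection a condition of taking part, and it ties the staining to the hypothesis, which can only be addressed by comparing arms.

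A second reply concerns direction. A reader might infer that the more effective steroid will look worse under the microscope. The documents do not support that. It needs a positive correlation between pathology and failure, and steroids that alter tissue little or not at all, whereas the Background describes the condition as inflammation of the tendons. Step 5 gives the right sign, attenuated. Patient choice also affects who has surgery, which clouds the sign further. This reply stands: reversal is possible, not predicted.

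Third, imprecision may matter more than bias. At ρ = 0.5 the spurious 0.30 SD is 0.298/0.439 = 0.68 standard errors, so a significant result would arise about 10% of the time instead of 5%. This is fair, but it is a further reason why the data cannot test the hypothesis.

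Two other readings go too far. The counts of 7 and 20 are not upper limits: they are expected numbers of patients, and because injection is into the affected digit or digits, one patient could give several specimens. Nor is it established that specimens mix one and two injections. Collection is tied to the end of the study, and it is unclear whether tissue from patients who refuse at 6 weeks and then have surgery is included.

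**Conclusion.** The statement is wrong as written, but only for the histology. A between-arm contrast in tissue from surgical patients is conditioned on a post-randomisation event that treatment is expected to change, and it has no comparator tissue. That conclusion needs no assumed correlation.

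The size and sign of the distortion do need assumptions that the documents do not supply. It ranges from 0.42 SD against the better arm (ρ = 0.7, no tissue effect), through roughly nothing (ρ near zero), to a true benefit shrunk from 0.76 to 0.16 SD. The expected 7 v 20 patients rest on equal allocation and on all failures having surgery. Failures who do not have surgery or are lost would lower them.

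A reader might infer that the trial's efficacy conclusion is compromised. It is not: the surgery outcome can still be compared in all randomised patients, and nothing here touches that analysis.

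**What to change.** In Specimen Collection:

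- Delete the final seven words of "effects of injections on treated tissue in order to effectively test the hypothesis".
- State that histology is exploratory and descriptive among patients who had surgery. Report it by arm with the number and share of randomised patients contributing tissue, the number of injections received, and baseline severity (QuickDASH and PROMIS are already completed before injection).
- State that the efficacy hypothesis is tested only by the primary outcome in all randomised patients, and that no histology difference between arms will be taken as evidence of efficacy.
- Clarify whether tissue is included from patients who refuse the second injection at 6 weeks and then have surgery.

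The cost is a wording amendment, with no added procedures or patients. The small downside is giving up a confirmatory claim that these data could not support.
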